Title: COVID-19 Antibody and Reinfection Study

NCT number: 1589316-19

Revised: 8/1/2023

STUDY PROTOCOL AND STATISTICAL ANALYSIS PLAN

Goal:

The goal of this study is to establish a cohort of Kaiser Permanente Colorado (KPCO) members who have and have not had COVID-19 infection for serial antibody testing and PCR testing to:

- 1. Quantify antibody titers among participants over 9 months.
- 2. Determine the rates of recurrent infection among participants with prior COVID-19.
- 3. Examine association between antibody titer levels and risk of recurrent infection.

Description:

In this study, the Kaiser Permanente Colorado (KPCO) Institute for Health Research (IHR) will evaluate SARS-CoV-2 IgG antibody titers over time and correlate antibody titers with risk of recurrent infection. The investigators will identify KPCO members who have and have not had prior infection, enroll them into a cohort study, conduct serial surveys for new COVID-19 symptoms, and facilitate serial viral and antibody testing.

All laboratory testing procedures and clinical management of participants will be conducted by KPCO operations. The research team will identify participants, obtain consent, administer surveys to assess COVID-19 symptoms, and direct patients to the appropriate testing. Health outcomes on cohort participants will be tracked with survey data on symptoms, clinical and utilization data from the KPCO electronic health record (e.g., hospitalization), and laboratory data (e.g., viral test results).

This research-operations partnership strategy will generate data to better understand the implications of positive antibody titers to this novel pathogen.

Study Type: Observational

Study Model: Case-control nested in a prospective cohort study We will recruit participants into a prospective survey and testing cohort who had suspected or confirmed SARS-CoV-2 infection. We will also recruit randomly sampled patients of similar age, sex, and race/ethnicity with no evidence of previous SARS-CoV-2 infection.

Time Perspective: Prospective

Target Follow-up: 10 months

Study Population:

The study population will include individuals who are enrolled in KPCO's health plan. Individuals will be selected who have evidence of prior SARS CoV-2 infection and samples of the general KPCO membership of similar demographic characteristics who appear not to have had SARS CoV-2 infection.

Inclusion criterion:

- KPCO health plan members,
- 18 years and older,
- Have a valid email address or phone number in the electronic health record.

Exclusion criterion:

- Opted out of research
- Participated in the pilot survey

Need a non-English language interpreter

HIPAA Privacy Rule Authorization and Informed Consent Process:

This study will ask for a waiver of HIPAA Privacy Rule Authorization to identify KPCO members who meet the inclusion and exclusion criteria (see above). It is not feasible to outreach this cohort without the waiver as the study will include large numbers.

This study will consent eligible members. Participants will be consenting to serial surveys, receipt of messaging about testing, and access to antibody testing. This study will consent patients electronically through the REDCap e-consenting process. They will also authorize study staff to track COVID-19 tests performed, testing results, risk factors for severe COVID-19 disease, and health outcomes. Participants' EHR data 24 months prior to enrollment into the study and up to 24 months after completing the study may be included the analyses.

Study Procedures:

After identifying and consenting members, we will administer a REDCap initial survey to inquire about current symptoms of COVID-19, prior symptoms of COVID-19, prior testing for COVID-19 (and results), prior or current quarantine or isolation, interest in getting tested, attitudes about testing, self-protective behaviors (e.g., social distancing, mask wearing), demographic information, employment category, and contact with patients or the public through their employment. We anticipate that the survey will take 10 minutes to complete. Follow-up surveys, conducted every 28 days, will inquire about new symptoms, new testing, current attitudes and current behaviors. Testing procedures and patient notification of viral and antibody results will be conducted by operations as part of routine medical care. Operations has notified us that antibody results will be made available on KP.org or the KP app. We will inform participants that they can obtain results there.

At the time of the baseline or follow-up surveys, based on the responses to questions about prior testing and symptoms on the surveys, individuals will be encouraged to seek viral or antibody testing.

Participants will receive a thank you email and a second email with instructions for obtaining viral and/or antibody testing, depending on their reported previous test(s) and result(s), and symptoms.

Participants will be sent a follow-up REDCap survey every 28 days to track symptoms, testing and results, quarantine or isolation, attitudes about testing, and protective behaviors. After follow-up survey completion, participants will be provided the same instructions about testing, based on their responses, as for the baseline. We will conduct repeat antibody testing on individuals who test positive to assess for reductions in titer levels over time, and among individuals who have negative antibodies to see if they develop new evidence of infection. We will conduct repeat viral testing among individuals who report no symptoms in order to assess for new asymptomatic infections.

Upon completion of the study, all participants will be sent an "Exit Survey" and testing opportunity. After completing the survey, participants will be asked to complete a final nasal and antibody test as part of the study.

Protocol Revisions:

Within this cohort, we opted to conduct a nested case-control analysis to examine the association between antibody status and reinfection. A nested case-control analysis was selected to account for the complexities of pandemic changes over time and various vaccines used during the study period. In addition, antibody status (positive/negative) was used instead of titer levels, as titer ranges differed across test types.

Data Analysis:

We will describe the antibody testing results and rates of reinfection among the study participants. We will use a nested case-control study design to examine the association between antibody seronegativity and reinfection. Reinfection will be defined as a positive SARS-CoV-2 RNA test ≥ 90 days after the first positive RNA test. Participants with reinfections will be matched to controls without reinfections by age, sex, date of the first positive RNA test, date of the last serology test, and serology test type. Using conditional logistic regression, case patients will be compared to control patients on the last serologic test result, with adjustment for potential demographic and clinical confounders.

Privacy, Confidentiality and Data Security:

The primary protection against a breach of privacy and confidentiality is in the structure of the data itself. The data extracted will include the minimum necessary to conduct the described research. Additional procedures will be in place to further protect members from a breach of confidentiality: 1) all data in study datasets will be identified only by a study-assigned unique ID number and will not include the medical record number of the subject; 2) a crosswalk table linking the study ID to a patient medical record number will be separately maintained on password-protected computers only accessible to study staff; 3) members of the study team have completed mandated training procedures and certifications, including special compliance training; new research team members (if any) will complete currently mandated training procedures and certifications prior to working on the study; and 4) the study protocol will be reviewed, approved, and monitored by the IRB. Furthermore, only aggregate data will be released in any public forum or publication.

Risks and Benefits:

This study includes surveys, information about COVID-19 viral and antibody testing, and prompts to get viral or antibody testing, including earlier access to antibody testing being offered at KPCO.

Participation in the study may give participants with symptoms messaging to get viral testing, which may be beneficial for their health and the health of their close contacts. For participants who do not have symptoms, they may learn they have been exposed to COVID-19 through antibody testing. The harms and benefits of obtaining this information are currently unknown. Participants are free to choose whether to get testing. Testing is not a requirement for participation. Testing procedures and medical management will be conducted by KPCO operations.

The primary risk of this study is the potential for loss of confidentiality and privacy of a member, through a loss or inappropriate disclosure of study data. Providing information about a member's COVID-19 symptoms, testing and attitudes may make them feel uncomfortable. They can choose to only answer questions that they are comfortable answering. Additionally, there is also a small risk for discrimination among individuals who have a positive viral test, a negative or positive antibody test, and/or a change in employment location or duties if they disclose the results to their employer. Research staff will not disclose the results of any testing conducted among individual participants to their managers. There are some inherent physical risks in

testing from nasal swabs and blood draws. Finally, the tests KPCO makes available may be under Emergency Use Authorization and any results should be interpreted with caution. Although we will advise them not to, participants may change their behavior as a result of positive antibody test results and could put themselves or others at risk for infection if the test is inaccurate. Alternatively, participants may have an increase in anxiety if their test results are positive or negative. All of these risks described are considered minimal.

There are no known risks to investigators or staff. The benefits outweigh the minimal risks to participants.

Compensation to Participants:

No compensation will be provided to participants.

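### Does the nested case-control analysis leave individual vaccination uncontrolled, although vaccines are a stated reason for choosing that design?

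*Combined protocol and SAP*

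**What the plan says.** Protocol Revisions gives the reason for the design: "A nested case-control analysis was selected to account for the complexities of pandemic changes over time and various vaccines used during the study period". It is the only place where the document mentions vaccines.

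The Data Analysis section supplies two means of control. Participants with reinfection are matched to controls "by age, sex, date of the first positive RNA test, date of the last serology test, and serology test type". In a conditional logistic regression, "case patients will be compared to control patients on the last serologic test result, with adjustment for potential demographic and clinical confounders". The covariates are not listed.

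On data sources, the section on HIPAA authorization and consent says that participants' "EHR data 24 months prior to enrollment into the study and up to 24 months after completing the study may be included" in the analyses. Under Study Procedures, the baseline survey covers "self-protective behaviors (e.g., social distancing, mask wearing), demographic information, employment category, and contact with patients or the public through their employment" among other topics, and the 28-day follow-up surveys "will inquire about new symptoms, new testing, current attitudes and current behaviors". Vaccination is not among the listed survey topics or the items that participants authorize staff to track.

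**The concern.** Matching on calendar dates lines up a case and its control on vaccine availability, and matching on test type keeps assay differences out of the comparison. Neither makes the two people alike in whether, when or with which product they were vaccinated. Vaccination can lower the risk of reinfection through routes other than the measured antibody. Where the assay responds to vaccine antibody, it also makes a negative result less likely. Left out of the model, it could therefore make seronegativity look harmful when it is not, or exaggerate a real effect.

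A second worry is timing. The exposure is the last serology result, and no rule covers a dose given between that test and the reinfection. A person recorded as seronegative may no longer be so when the outcome occurs.

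A lesser worry is that protective behaviour and public-facing work are collected but do not sit clearly under demographic or clinical confounders.

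At stake is whether the reported odds ratio reflects antibody status or vaccination.

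**Working it through.** The documents give no sample size, event count, vaccination coverage, seronegativity rate or assay target, so there is no stated figure to reproduce. Every input below is an assumption, used only to show possible size.

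**1. Vaccination before the serology, omitted from the model, no matching.** Let *v* be the share vaccinated (30–80%), *s₀* and *s₁* the seronegative shares among the unvaccinated (15–25%) and vaccinated (3–10%), *r* the reinfection risk if unvaccinated (10%), and *k* the vaccine risk ratio (0.3–0.7). Serostatus has no effect within either vaccination group, so the true OR is 1.

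- Seronegative cases: a = (1−v)s₀r + v s₁kr
- Seropositive cases: b = (1−v)(1−s₀)r + v(1−s₁)kr
- Seronegative non-cases: c = (1−v)s₀(1−r) + v s₁(1−kr)
- Seropositive non-cases: d = (1−v)(1−s₀)(1−r) + v(1−s₁)(1−kr)

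At the midpoints (v = 0.55, s₀ = 0.20, s₁ = 0.065, k = 0.5):

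- a = 0.45×0.20×0.10 + 0.55×0.065×0.05 = 0.01079
- b = 0.45×0.80×0.10 + 0.55×0.935×0.05 = 0.06171
- c = 0.45×0.20×0.90 + 0.55×0.065×0.95 = 0.11496
- d = 0.45×0.80×0.90 + 0.55×0.935×0.95 = 0.81254
- OR = ad/(bc) = 1.24

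Over the full grid the OR runs from 1.03 (v = 0.30, 15% vs 10%, k = 0.7) to 1.94 (v = 0.80, 25% vs 3%, k = 0.3). At baseline risks of 2% and 20% the midpoint is 1.22 and 1.26. With equal seronegativity in the two groups it is 1.00.

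**2. Credit for date matching.** The plan does match on dates, so this is the relevant comparison. Use the same model in ten equal calendar periods with linearly rising coverage. The 1:1 matched OR is Σ[ad/(c+d)] / Σ[bc/(c+d)], summed over periods. The extremes use the other inputs at the ends given in step 1.

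| Coverage over time | Unmatched OR, midpoint | Date-matched OR, midpoint | Date-matched OR, extremes |
|---|---|---|---|
| 30% to 80% | 1.24 | 1.21 | 1.04–1.56 |
| 0% to 90% | 1.20 | 1.13 | 1.03–1.31 |

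Date matching alone removes about 11–14% of the excess in the first pattern and 34–40% in the second. Adjusting for vaccination as well returns 1.00, because the model has no serostatus effect within vaccination groups.

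**3. Doses after the last serology.** Assume an undosed seropositive risk of 5%, and a risk of 2.5% after a dose whatever the earlier result.

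- *Equal uptake, true OR 2.0.* The undosed seronegative odds are 2×0.05/0.95, a risk of 9.52%. With 30% dosed, the risks are 0.7×9.52% + 0.3×2.5% = 7.42% and 0.7×5% + 0.3×2.5% = 4.25%, so the OR is 1.80. With 10% and 50% dosed it is 1.94 and 1.64.
- *Unequal uptake, true OR 1.0.* With 60% of seronegatives and 40% of seropositives dosed, the risks are 0.4×5% + 0.6×2.5% = 3.5% and 0.6×5% + 0.4×2.5% = 4.0%, so OR = (0.035/0.965)/(0.040/0.960) = 0.87. With the shares reversed it is 1.15.

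Dilution therefore holds for equal uptake but not in general; the direction depends on who is dosed.

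**4. What the text commits to.** The figures in step 2 describe an analysis that matches on dates and omits vaccination. The plan promises matching together with adjustment "with adjustment for potential demographic and clinical confounders". Vaccination fits that description, and the health-record window permits data that could supply it.

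**The case for a change.** The strongest case for a change is that vaccines are the one clinical factor the plan cites as a reason for its design, yet no step names vaccination. Silence leaves the choice of covariates open until results are seen. Vaccination is not a listed survey topic or tracking item, the record access is permissive, and the document does not say how completely the record captures doses. The assay targets are not given either, so one cannot assume that the path through the serology result is absent.

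Much of this is true as description. The matching factors do not balance individual vaccination, and a reader cannot confirm from the text that it will be in the model. But this shows missing detail rather than a wrong analysis. The sentence on the design's purpose does not say that matching alone controls vaccination; matching plus covariate adjustment is its natural reading.

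On later doses, the exposure is stated plainly: "case patients will be compared to control patients on the last serologic test result". If the question is how that result relates to subsequent reinfection, a later dose is part of what follows. Participants can see their results, so uptake may respond to them, and an indicator for later doses would condition on a possible consequence of the exposure. Including or omitting it is a choice between estimands, each with a cost.

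Reporting by vaccination stratum, listing assay targets and adding behaviour items are reasonable preferences, but no error depends on them.

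**Conclusion.** The concern does not call for a change. The plan commits to confounder adjustment in the conditional logistic model, and vaccination is a covariate that a competent analyst would include given the plan's own rationale. Naming it would add transparency without altering the analysis that the text already supports.

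This rests on two assumptions: that vaccination is treated as a clinical confounder, and that the health record supplies it adequately. If it were omitted, the assumed inputs put the spurious OR after date matching at about 1.03 to 1.56, with 1.13 or 1.21 at the midpoints, and 1.00 where the assay does not respond to vaccination. The documents cannot narrow that range. For doses after the serology, neither the direction nor the size of any distortion is established (0.87 or 1.15 under a true OR of 1.0, depending on which group is dosed more), and the handling is a fair trade-off.

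### Data Analysis has no rule for positive viral tests reported in the 28-day surveys: such participants can be drawn as controls, and the Goal 2 reinfection rate may be understated

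*Combined protocol and SAP*

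**What the plan says.** The case definition is in the Data Analysis section: "Reinfection will be defined as a positive SARS-CoV-2 RNA test", at least 90 days after the first such positive. No other test type or source is named, and the text does not say whether an RNA positive known only from a survey would qualify. Cases are to be "matched to controls without reinfections" on age, sex, two dates and serology test type. Controls need no negative RNA test, and a reported positive does not exclude them.

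Under Study Procedures, "Participants will be sent a follow-up REDCap survey every 28 days to track symptoms, testing and results". The type of test is not specified.

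The reinfection rate is an output in its own right. Goal 2 is to "Determine the rates of recurrent infection among participants with prior COVID-19", and Data Analysis repeats that the rates will be described. Neither place says how a survey-reported positive is handled: counted, confirmed, excluded from controls, or used in a sensitivity analysis.

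**The concern.** Two decisions are folded into one definition. Requiring an RNA positive to be a case protects specificity. Treating everyone else as free of reinfection is a separate decision, and the plan takes it by default. Under the text as it stands, a participant who reports a positive viral test in month 5 and never has a qualifying RNA test is an eligible control and contributes no event to the rate.

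Two results are exposed. The Goal 2 rate would be an RNA-confirmed rate presented as the reinfection rate. The control group could include some people who were reinfected, which shifts the odds ratio for seronegativity.

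**Working it through.** **Figures in the plan.** The documents give no expected reinfection rate, odds ratio, sample size or control-to-case ratio, so there is nothing to reproduce. What follows is an illustration on assumed inputs, ignoring the matching.

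**Assumed inputs.**
- R, true reinfection risk: 2% to 20%.
- s, share of true reinfections with a qualifying RNA positive: 0.9 to 0.5.
- Seronegative share among the truly non-reinfected: 20%, so odds 0.25.
- True odds ratio: 2 or 3.

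**Formulas.**
- Observed rate = R × s, so the relative understatement is 1 − s.
- Truly reinfected share of the control pool: c = R(1 − s)/(1 − Rs).
- Observed odds ratio = odds of seronegativity in cases ÷ odds of seronegativity in the mixed control pool.

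**One case in full (R = 10%, s = 0.7, true odds ratio 2).** Observed rate = 0.10 × 0.7 = 7%. c = 0.03/0.93 = 3.2%. Case odds = 2 × 0.25 = 0.50, so one third of cases are seronegative. Control seronegativity = 0.0323 × 0.3333 + 0.9677 × 0.20 = 0.2043, odds 0.2568. Observed odds ratio = 0.50/0.2568 = 1.95.

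**Range, with s the same in both serostatus groups.**

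| R | s | Observed rate | Contaminated controls | 2.00 reads | 3.00 reads |
|---|---|---|---|---|---|
| 2% | 0.9 | 1.8% | 0.2% | 1.997 | 2.99 |
| 10% | 0.9 | 9% | 1.1% | 1.98 | 2.95 |
| 10% | 0.7 | 7% | 3.2% | 1.95 | 2.87 |
| 10% | 0.5 | 5% | 5.3% | 1.92 | 2.79 |
| 20% | 0.5 | 10% | 11.1% | 1.83 | 2.58 |

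The rate is affected more than the odds ratio. At R = 10% and s = 0.7 the rate is 30% too low in relative terms, while the odds ratio moves by under 3%.

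**If s differs by serostatus (R = 10%, true odds ratio 2).**
- s = 0.9 in seronegatives and 0.6 in seropositives. Cases: 0.10 × 1/3 × 0.9 = 0.030 seronegative and 0.10 × 2/3 × 0.6 = 0.040 seropositive. Controls: 0.18 + 0.0033 = 0.1833 and 0.72 + 0.0267 = 0.7467. Odds ratio = 0.75/0.2455 = 3.06 (3.055 unrounded). With all missed reinfections removed from the controls it is 0.75/0.25 = 3.00.
- s = 0.6 and 0.9. Cases: 0.020 and 0.060. Controls: 0.1933 and 0.7267. Odds ratio = 0.3333/0.2661 = 1.25; with clean controls, 0.3333/0.25 = 1.33.

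In both directions most of the bias comes from which reinfections become cases, so cleaning the controls leaves it largely in place.

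**The case against.** An RNA-only outcome is defensible. It is specific, and it fits the stated aim of serial PCR testing and the use of laboratory data as an outcome source. The design also limits missed reinfections: survey answers lead to testing instructions, repeat viral testing is planned in people without symptoms, and everyone is asked for a nasal test at exit. All of that stands, and it is a reason to keep the case definition. It does not close the gap. The Risks and Benefits section makes testing voluntary, nothing says that a reported positive leads to a confirmatory RNA test, and one swab at exit cannot be assumed to find infections from earlier in a 10-month follow-up.

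A reader might infer four stronger things that the documents do not support.
- **That the surveys are known to collect antigen or home-test results.** The text names no test type. A reported positive could be the same RNA test, an antibody test, a false positive, or a result inside the 90-day window.
- **That the rate is understated as a matter of fact.** This requires true reinfections that never received a qualifying RNA test. That is plausible, but not shown. Nor is the RNA rate a strict lower bound, since false-positive RNA results are possible.
- **That the odds ratio is materially pulled toward 1.** Contamination of 5% to 20%, with 60% to 90% RNA capture, needs R = c/[(1 − s) + cs]. That runs from 0.05/0.43 = 12% to 0.20/0.28 = 71%, and nothing in the documents supports risks across that range. The direction also holds only if detection is unrelated to serostatus. Participants can see their antibody results online, so testing behaviour could differ.
- **That controls with any positive test should be dropped.** Serology is the exposure. If a fraction q of seropositive controls had a positive antibody test in the exclusion window, dropping them multiplies the odds ratio by 1 − q. With q = 0.5 (assumed), 2.0 becomes 1.0, which is worse than the contamination being corrected.

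**Conclusion.** The gap is real and minor. As written, a participant with a survey-reported positive viral test and no qualifying RNA result is an eligible control and is not counted under Goal 2. The main consequence is for the rate: it may be understated by a relative 1 − s, and s is unknown. The effect on the odds ratio is probably small when RNA detection is unrelated to serostatus: a true 2.00 reads 1.997 to 1.83 over the whole assumed range, and about 1.95 at 10% risk and 70% capture. If detection depends on serostatus, the error can be larger and in either direction, and no rule about controls repairs it. All sizes rest on assumed R, s and seronegative share and on ignoring the matching. They also count every missed reinfection, whereas the surveys can reveal only those that were tested and reported.

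**What to change.** Keep the RNA-positive case definition and make these changes in Data Analysis.

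1. State which sources and test types count, including whether an RNA positive reported only by survey qualifies.
2. Exclude from the control pool anyone with a survey-reported or recorded positive viral test from day 90 after the first positive RNA test to the matched index date. Limit this explicitly to viral tests. The plan names no index date, so define it, for example as the date of the matched case's qualifying RNA positive.
3. Report the Goal 2 rate twice: RNA-confirmed, and RNA-confirmed plus survey-reported positive viral tests at least 90 days after the first RNA positive.
4. Tabulate RNA testing frequency by serostatus, so that readers can judge whether detection differed. This does not correct such a difference.

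The cost is a few sentences and one extra rate from information the surveys already collect, provided the survey responses identify the test as viral. Some controls will be lost to unverified self-reports. The second rate is less specific, so it should stand beside the RNA-confirmed rate and not replace it.

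### The serology exposure has no index date, so the rule as written admits tests taken after reinfection and can bias the odds ratio, plausibly but not certainly downward

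*Combined protocol and SAP*

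**What the plan says.** The comparison is defined in the Data Analysis section of the combined protocol and SAP: "case patients will be compared to control patients on the last serologic test result", by conditional logistic regression. Age and sex are matched, and the remaining matching factors are "date of the first positive RNA test, date of the last serology test, and serology test type". The outcome is dated: "Reinfection will be defined as a positive SARS-CoV-2 RNA test ≥ 90 days after the first positive RNA test". That date is not used to limit which serology counts. Controls are described only as participants without reinfection, with no reference date of their own.

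Other sections determine which tests could be the last one:

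- Study Procedures provides for repeat antibody testing, including "among individuals who have negative antibodies to see if they develop new evidence of infection".
- At study end, after the exit survey, "participants will be asked to complete a final nasal and antibody test as part of the study".
- The consent section says that "EHR data 24 months prior to enrollment into the study and up to 24 months after completing the study may be included the analyses".
- Test instructions are sent "depending on their reported previous test(s) and result(s), and symptoms", and Risks and Benefits makes testing voluntary.

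**The concern.** If a case's last serology was drawn after the reinfection, its result may be a consequence of the outcome. The plan itself retests antibody-negative people because it expects new infection to show in serology. A case who was seronegative before reinfection and positive at the exit test would be recorded as seropositive.

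This exposure carries the only comparative analysis in Data Analysis, the one that serves Goal 3 (antibody and risk of recurrent infection). An OR built partly on post-outcome tests cannot be read as the risk of reinfection given earlier serostatus. Two programmers following the text could also choose different tests for the same case and obtain different ORs.

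**Working it through.** **Order of events.** The plan gives no OR, seronegativity rate or number of reinfections, so there is no figure to reproduce. The first check is on timing.

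1. The exposure is the last test, with no end date attached.
2. The exit antibody test is requested of all who complete the exit survey. For anyone reinfected earlier in the study, it follows the outcome. Health-record results after completion can be later still.
3. Matching on serology date does not exclude this. A case and a control who both had exit tests in the same week satisfy the matching rule, and the case's test still follows the reinfection.

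Post-reinfection serology is therefore admissible as written. How often it would occur cannot be found from the documents.

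**Direction and size, by illustration.** Every input is assumed:

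- p0 = 0.15, share of controls seronegative at the reinfection date
- q = 0.30, share of cases seronegative before reinfection
- f = 0.5, share of last tests taken after the reinfection date, the same in controls because serology dates are matched
- s and c, the shares of seronegative cases and controls that turn positive by a late test

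Seropositive people are assumed to stay positive, and f is assumed independent of serostatus.

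True OR = (0.30/0.70) / (0.15/0.85) = 0.4286/0.1765 = 2.43.

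Observed OR = odds[q(1 − f·s)] / odds[p0(1 − f·c)].

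| s (cases) | c (controls) | Cases observed negative | Controls observed negative | Observed OR |
|---|---|---|---|---|
| 50% | 0% | 0.30 × 0.75 = 0.225 | 0.15 | 0.2903/0.1765 = 1.65 |
| 50% | 25% | 0.225 | 0.15 × 0.875 = 0.131 | 0.2903/0.1511 = 1.92 |
| 50% | 50% | 0.225 | 0.15 × 0.75 = 0.1125 | 0.2903/0.1268 = 2.29 |
| 30% | 50% | 0.30 × 0.85 = 0.255 | 0.1125 | 0.3423/0.1268 = 2.70 |

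With no true association (q = 0.15), the same four rows give:

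- 0.1268/0.1765 = 0.72
- 0.1268/0.1511 = 0.84
- 0.1268/0.1268 = 1.00
- 0.15 × 0.85 = 0.1275, odds 0.1461; 0.1461/0.1268 = 1.15

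Equal conversion preserves the ratio of proportions (0.225/0.1125 = 2) rather than the OR. That is why the third row falls slightly short of 2.43 although the null case stays at exactly 1.

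**Effect of matching.** The table is marginal. In 1:1 pairs where late tests fall in the same pairs, the conditional OR is Σq(1−p)/Σp(1−q), where q and p are the case and control shares observed negative in each kind of pair. The second row becomes (0.15 × 0.8875 + 0.30 × 0.85)/(0.1125 × 0.85 + 0.15 × 0.70) = 0.3881/0.2006 = 1.93. The third becomes (0.15 × 0.925 + 0.255)/(0.075 × 0.85 + 0.105) = 0.3938/0.1688 = 2.33. The pattern is unchanged.

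**The case against.** The best defence is that the intended meaning is clear. The case-control analysis is nested in a prospective cohort, Goal 3 speaks of risk, and matching on first-positive date and serology date makes most sense for a test taken before the outcome. This stands as a statement of probable intent. A reader might infer that the sponsor chose to use post-reinfection serology, and the documents do not support that. They show that the limit is unwritten.

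A second objection concerns direction. A reader might infer that the OR must be biased downward, or that a true OR of 1 must appear below 1. Both hold only if controls convert less than cases. Because controls are matched on serology date, their late tests also allow time for change. Protocol Revisions notes that several vaccines were in use, and Study Procedures retests antibody-negative people. This objection stands: the last row of the table moves upward.

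Third, post-reinfection testing may be rare, since it is voluntary and instructions depend on earlier results and symptoms. That is possible but cannot be shown either way, and a cut-off makes the question unnecessary.

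**Conclusion.** The concern holds and should be fixed. The exposure rule sets no limit relative to the reinfection date, the planned testing makes later serology foreseeable, and matching on serology date does not restore the order.

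Downward bias is plausible, because reinfection is an added antigen exposure that non-reinfected controls do not have. It is conditional on cases converting more than matched controls over the same interval. With comparable conversion the bias is small or nil, and with sufficiently greater conversion in controls it is upward.

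The size cannot be found from the documents. The illustrative span of 1.65 to 2.70 around a true OR of 2.43 rests wholly on assumed inputs. It shows that both directions are possible and does not bound the trial's error. Confidence is high that the time limit is missing, and lower about the direction of bias.

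**What to change.** In Data Analysis:

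1. Define the index date as the date of the case's reinfection RNA test, and assign it to the matched controls.
2. Define exposure for both as the most recent serology collected after the first positive RNA test and before the index date. The lower limit is needed because the cohort also enrols people with no evidence of earlier infection, whose pre-infection negative result would otherwise count as seronegative.
3. Match on the date and type of that test.
4. Exclude serology on or after the index date, including exit tests and later health-record results.

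The present definition of controls as participants without reinfection can stay. Sampling controls from those still at risk at the index date, including some reinfected later, is a separate and optional design choice.

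The cost is wording and data-set programming. No new data collection is needed, because participants already "authorize study staff to track COVID-19 tests performed, testing results". If the analysts already restrict to pre-reinfection tests, stating the rule settles the timing.

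The downside is that cases with no eligible serology are lost, and their number is unknown. By the reinfection definition the window is at least 90 days, and health-record serology from before enrolment may reduce the loss. Included cases may over-represent people who test often, so report the number excluded and compare them with those included.
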